### 7.3.3 Erdafitinib

Erdafitinib is an investigational product manufactured and provided by Janssen Research & Development, as film-coated tablets of 3, 4 and 5 mg. Administration is performed on an outpatient, self-administration basis, at a stipulated starting dose based on the escalation cohort level. Tablets should be swallowed intact, once daily, with 240 mL of water (8 ounces), with or without food, at approximately the same time every day, in a 28-day cycle. For dose adjustments, see Dose Modification guidelines, Section 8.

If a dose is missed, it can be taken up to 6 hours after the scheduled time. Otherwise, that dose should be skipped and subject should continue treatment at the scheduled time the next day. Missed doses of erdafitinib should not be made up. For example, if a dose is vomited any time after taking erdafitinib, a replacement dose should NOT be taken. If a dose is entirely missed for one day, dose should be skipped and NOT made up the next day; patients should resume regular dosing as prescribed the following day. Patients who inadvertently take one extra dose during a day must skip the next day's dose. If patient takes more than two doses of erdafitinib in a day, the patient should bring this to the attention of his or her treating physician.

On days when patient is scheduled for a clinic visit, the patient should take scheduled erdafitinib dose once all visit assessments have been performed and are within acceptable range unless otherwise indicated. Patients should be instructed to record daily administration of the study drugs in the pill diary.

On days with PK sampling, additional guidelines should be followed:

- The pre-dose sample should be drawn before erdafitinib dosing
- On days and time points when PK, biochemistry, hematology or other blood samples are to be performed, the PK sample must be drawn first
- The sampling time of the pre-dose PK sample and the dosing time of erdafitinib from the day before and current day must be precisely recorded
- If vomiting occurs, the exact time of the first vomiting episode within the first 4 hours post-dosing on that day must be noted
- Time of administration of gastric protection agents on days of PK sampling should be precisely recorded

### 7.4 Definition of Dose-Limiting Toxicity (DLT)

Any of the following events that occur during cycle 1 (first 4 weeks) will be considered a DLT when classified as possibly, probably or definitively related to investigational study treatment (according to NCI CTEP Adverse Event Reporting Requirements). Apart from the criteria listed below, if a lower grade AE leads to a dose interruption of more than 21 consecutive days of erdafitinib for the first 4 weeks of Cycle 1, this AE will be considered a DLT; patients must receive at least 75% of study drug during cycle 1 in order to be evaluable for the DLT observation period. Whenever a patient experiences toxicity that fulfills the criteria for a DLT, treatment with the study drug responsible for the toxicity will be interrupted (patient may continue the remainder study drugs) and the toxicity will be followed up. The Protocol Chair must be notified immediately of any DLT:

TOXICITY	DLT CRITERIA
Blood and lymphatic system disorders	Anemia CTCAE Grade $\geq$ 3 will not be considered DLT unless judged to be a hemolytic process secondary to erdafitinib.
	Febrile neutropenia CTCAE Grade $\geq$ 3
	ANC CTCAE Grade 3 for > 14 consecutive days
	ANC CTCAE Grade 4
	Platelet count CTCAE Grade 3 for > 7 consecutive days and/or with signs of bleeding
	Platelet count CTCAE Grade 4
Ocular disorders	CTCAE Grade $\geq$ 2 for > 21 days CTCAE Grade $\geq$ 3
General disorders and administration site conditions	Fatigue CTCAE Grade 3 for > 7 consecutive days
Skin and subcutaneous tissue disorders	Skin, mucosal or nail toxicity CTCAE Grade $\geq$ 3 for > 72 hours
Hyperphosphatemia	Phosphorus level $\geq$ 7.0 mg/dL for > 14 days despite treatment
GI disorders a	Diarrhea CTCAE Grade $\geq$ 3 for $\geq$ 48 hrs, despite the use of anti-diarrhea therapy
	Nausea/vomiting CTCAE Grade $\geq$ 3 for $\geq$ 48 hrs, despite the use of anti-emetic therapy
	Constipation CTCAE Grade $\geq$ 3 for $\geq$ 48 hrs, despite the use of anti-constipation therapy
Investigations b	Blood bilirubin c CTCAE Grade 2 for > 7 consecutive days or $\geq$ Grade 3
	AST or ALT CTCAE $\geq$ Grade 3
	Alkaline phosphatase CTCAE $\geq$ Grade 3
Other hematologic and non-hematologic toxicities	Any other CTCAE $\geq$ Grade 3 toxicity for > 7 consecutive days (except decreased lymphocyte count [lymphopenia] that is not clinically significant)

TOXICITY	DLT CRITERIA
	
a Patients will not initially receive prophylactic treatment for nausea/vomiting during Cycle 1. However, prophylactic treatment may be initiated in all patients at the dose level where these toxicities have been observed and in all further patients if at least 1 patient has experienced nausea/vomiting CTCAE Grade <math>\geq</math> 3 or if at least 2 patients experienced nausea/vomiting CTCAE Grade <math>\geq</math> 2. However, anti-emetics may be applied for treatment if the patient has experienced nausea/vomiting CTCAE Grade <math>\geq</math> 1 at the discretion of the treating physician.
 
b For any hepatic toxicity CTCAE Grade 4, or CTCAE Grade 3 that does not resolve within 7 days to CTCAE Grade <math>\leq</math> 1 (or CTCAE Grade <math>\leq</math> 2 if liver infiltration with tumor present), an abdominal CT scan should be performed to assess if it is related to disease progression.
 
c Refers to total bilirubin.

	
Apart from the criteria listed above, if a lower grade AE leads to a dose interruption of more than 14 consecutive days of erdafitinib, this AE may be considered as DLT (the determination will be based on clinical significance and patient risk; discussion with the Protocol Chair will determine if the event should or should not count as a DLT).

Patients whose treatment is interrupted or permanently discontinued due to an AE or clinically significant laboratory value, must be followed as outlined in the table below, at least once a week for 4 weeks, and subsequently at 4-week intervals, until resolution or stabilization of the event, whichever comes first. Patients that require a dose delay of  $> 28$  days due to a cause unrelated to study participation will have the opportunity to continue study if deemed eligible to do so by the Protocol Chair of the study.

TOXICITY	FOLLOW-UP EVALUATION
Hematology	If $\geq$ CTCAE grade 3 neutropenia or $\geq$ CTCAE grade 3 thrombocytopenia have been demonstrated, these parameters must be repeated at least once a week until resolution to $\leq$ CTCAE grade 1 neutropenia or $\leq$ CTCAE grade 1 thrombocytopenia to allow for initiation of re-treatment.
Renal	If creatinine $\geq 2 \times$ ULN has been demonstrated, this parameter must be evaluated at least twice a week until resolution to $\leq$ CTCAE grade 1 to allow for initiation of re-treatment, and then at least weekly until either resolution or until stabilization.  Creatinine $\geq 2.0 \times$ ULN and 3+ proteinuria or hematuria $\geq$ CTCAE grade 2 has been demonstrated, a 24-hour urine collection for total protein and total creatinine must be repeated at least weekly until either parameter returns to baseline value or until stabilization. Whenever a measured CrCl is obtained, a creatinine should be obtained within $\leq 72$ h of the urine collection.
Hepatic	If total bilirubin $\geq 2 \times$ ULN or $\geq$ CTCAE grade 3 AST/ALT has been demonstrated, these parameters must be repeated daily until resolution to $\leq$ CTCAE grade 1 (or $\leq$ grade 2 for AST or ALT, if liver metastasis are present) to allow for initiation of re-treatment, and then at least weekly until either resolution or until stabilization  Patients with total bilirubin $>$ ULN (any duration) should have fractionation of bilirubin into total/direct or indirect/direct components and any additional work-up as clinically indicated by

	these results. Follow-up of hyperbilirubinemia should proceed as per the guidelines above, irrespective of the results of fractionation.
Metabolic/Laboratory	Parameters of metabolic/ laboratory abnormalities $\geq$ CTCAE grade 3 must be assessed once at 2 to 4 days and once again at 7 days ( $\pm 1$ day) and be repeated twice a week until resolution to $\leq$ CTCAE grade 2 to allow for initiation of re-treatment, and then at least weekly until either resolution to $\leq$ CTCAE grade 1 or until stabilization.
	A CT scan or other imaging study to assess the pancreas, liver, and gallbladder must be performed within 1 week of the first occurrence of any $\geq$ CTCAE grade 3 of amylase or lipase levels.
	In patients with triglycerides $\geq 500$ mg/dL, urine amylase needs to be tested in addition.
Ocular toxicity	Patients who experience ocular toxicity should be followed as per Dose Modification guidelines (Section 8)
Non-Laboratory	Patients who experience non-laboratory DLTs must be evaluated at least once a week following demonstration of the toxicity until resolution of the toxicity to allow for re-treatment, stabilization of the toxicity, or study treatment completion.

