### 7.3 Agent Administration

The investigator will instruct the patient to take the study drugs as follows:

- Palbociclib: taken orally once daily, with food, for 21 days out of a 28-day cycle
- Erdafitinib: taken orally once daily, with or without food, at approximately the same time every day, in a 28-day cycle
- Fulvestrant: IM once every 28 days (except on cycle 1, when fulvestrant will also be administered on day 15). On the days that patients come in for clinic visit/ fulvestrant administration on even cycles (i.e. when tumor measurements or PKs are done), administration of palbociclib and erdafitinib should wait to be done in clinic.

A pill diary will be given to all patients enrolled in the study.

1 cycle = 28 days				
N of pts.	Dose Level	Fulvestrant (IM q28 days) §	Palbociclib* (PO daily x 21 out of 28 days)	Erdafitinib (PO daily)

3-6	3	500 mg	125 mg	8 mg
3-6	2	500 mg	125 mg	6 mg
3-6	1	500 mg	125 mg	5 mg
3-6	-1	500 mg	125 mg	4 mg

\* Palbociclib dose may be adjusted per standard of care clinical guidelines based on blood cell counts

§ On cycle 1, fulvestrant will also be administered on day 15 (loading dose)

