### **7.11 Replacement of Patients Who Discontinue Early**

In general, the study intends that patients would be treated until disease progression or intolerable toxicity. During the phase Ib dose escalation period and phase II portion of the study, if a patient discontinues study treatment for reasons clearly not related to study treatment, after completing fewer than one planned cycle of study, and/or receiving <75% of the total intended dose of study drugs over the first cycle of treatment, then that patient will be considered not evaluable and may be replaced with a new patient.

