## 17.2 Sample Size and Statistical Analysis

### 17.2.1 Primary endpoint

Demographic and baseline patient characteristics will be summarized. Adverse events will be classified by type, incidence, severity, and causality. All adverse events will be summarized by patient, dose level, and disease. All patients who received at least 4 weeks of study treatment drugs (unless DLTs observed) will be included in the **safety** portion of the trial, and all patients who received at least 8 weeks of erdafitinib will be included in the **tolerability** portion of the trial.

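### Section 7.4 requires 75% of study drug for DLT evaluability with no exception for patients who had a DLT, so its own interruption DLT fails the rule, and 17.2.1 says otherwise

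*Combined protocol and SAP*

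**What the plan says.** The sentence in section 7.4 that introduces the DLT criteria does two things. It makes an event a DLT "if a lower grade AE leads to a dose interruption of more than 21 consecutive days of erdafitinib" in the first four weeks, and after a semicolon it says that "patients must receive at least 75% of study drug during cycle 1 in order to be evaluable for the DLT observation period". The same paragraph directs that on any DLT "treatment with the study drug responsible for the toxicity will be interrupted". Below the criteria table, 7.4 adds a second, discretionary interruption DLT, settled in discussion with the Protocol Chair, "if a lower grade AE leads to a dose interruption of more than 14 consecutive days of erdafitinib".

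Two other sections bear on who is counted. Section 17.2.1, under the primary endpoint, puts in the safety portion of the trial "All patients who received at least 4 weeks of study treatment drugs (unless DLTs observed". Section 7.11 opens with discontinuation clearly unrelated to treatment, but goes on to "and/or receiving <75% of the total intended dose of study drugs over the first cycle of treatment", and lets a patient so described be called not evaluable and replaced.

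**The concern.** DLT in cycle 1 and the MTD are the primary endpoints. Escalation works on cohorts of three, so one patient's status can decide whether the dose goes up. A DLT normally stops the drug, which means that a minimum-exposure rule without a DLT exception falls hardest on the patients whose events the design needs to count. If those patients leave the denominator and are replaced, the observed DLT rate falls below the true one and the dose-finding rule leans towards escalation.

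**Working it through.** **Inputs.** Erdafitinib: "Erdafitinib: taken orally once daily, with or without food, at approximately the same time every day, in a 28-day cycle" (section 7.3), so 28 planned doses in cycle 1. Palbociclib: 21 doses. Fulvestrant: 2 administrations (Days 1 and 15). Total 28 + 21 + 2 = 51. From 17.2.1: target DLT rate 0.20, proper dosing interval 0.15 to 0.25, cohorts of 3; in the text, 0/3 is escalate, 1/3 is stay, and 3/3 is de-escalate and exclude the dose.

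**Step 1: reproduce the plan's decisions.** For each interval, the unit probability mass is the posterior probability of the interval divided by its length; the largest one sets the decision. The prior and the exclusion cutoff are not stated; Beta(1,1) and P(rate > 0.20) > 0.95 are assumed.

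| DLTs/patients | Escalate | Stay | De-escalate | Decision |
|---|---|---|---|---|
| 0/3 | 3.19 | 2.06 | 0.42 | Escalate |
| 1/3 | 0.73 | 1.52 | 0.98 | Stay |
| 0/2 | 2.57 | 1.92 | 0.56 | Escalate |

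For 3/3, P(rate > 0.20) = 0.998, so the dose is excluded. All three decisions given in the text reproduce. The zero-DLT row of Table 17.2.1 also shows escalate at two and at three patients.

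**Step 2: exposure after a hold.** With m erdafitinib days missed in cycle 1 and the other two drugs given in full, the largest possible exposure is as follows. The hold is taken to lie within cycle 1.

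| Reading of study drug | Formula | m = 22 (>21 days) | m = 15 (>14 days) | m = 8 |
|---|---|---|---|---|
| Erdafitinib doses | (28 − m)/28 | 6/28 = 21.4% | 13/28 = 46.4% | 20/28 = 71.4% |
| All administrations | (51 − m)/51 | 29/51 = 56.9% | 36/51 = 70.6% | 43/51 = 84.3% |
| Mean of the three drugs | ((28 − m)/28 + 1 + 1)/3 | 73.8% | 82.1% | 90.5% |

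The mandatory interruption DLT is below 75% on all three readings. The discretionary one fails on the first two. On erdafitinib doses the threshold is 0.75 × 28 = 21, so any listed DLT that stops erdafitinib for 8 or more days in cycle 1 also fails.

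**Step 3: effect on one cohort.** One DLT in three patients is stay. Remove that patient as not evaluable and the count is 0/2, or 0/3 if a replacement has no DLT. Both are escalate.

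**Step 4: effect on the chance of escalating.** Let p be the true DLT rate and q the share of DLTs lost and replaced. The documents give no value for q, so a range is shown. The rate among evaluable patients is p′ = p(1 − q)/(1 − pq), and the chance of 0/3 is (1 − p′)³. For p = 0.30 and q = 0.25: p′ = 0.225/0.925 = 0.243, and 0.757³ = 0.43.

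| True DLT rate | q = 0 | q = 25% | q = 50% |
|---|---|---|---|
| 20% | 51% | 60% | 70% |
| 30% | 34% | 43% | 56% |
| 40% | 22% | 30% | 42% |

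**The case against.** A reader might infer that the plan simply discards DLT patients. The documents do not support that. Section 17.2.1 sits under the primary endpoint and exempts patients with a DLT from its exposure requirement, and section 7.1 describes the safety profile as the assessment of DLTs and the MTD. Section 12.1 makes every patient evaluable for toxicity from the first dose. Section 7.11 can be read so that both exposure limbs qualify a discontinuation unrelated to treatment, and replacement there is optional. The likely intent is to keep DLT patients. This stands, and it limits the point to a conflict between sections. It does not remove the conflict, because 7.4 is the provision that defines DLT evaluability and it carries no exception.

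The mandatory route is also narrow. More than 21 consecutive days within 28 requires the hold to start by Day 7. The first scheduled visit after Day 1 is Day 8 (±3 days), and a hold over Days 8 to 28 is exactly 21 days. That stands as well, and it is a reason not to assume a large q.

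Three further inferences should be resisted.

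- That 75% means at most 7 missed days. This is so only on erdafitinib doses. Over all 51 administrations, 12 missed days still leave 39/51 = 76%.
- That replacing patients held for toxicity below DLT level lowers the DLT rate. Such a patient counts as a non-DLT, so replacement removes a zero. At a 30% rate with one such patient in three, the chance of 0/3 is 0.70² = 0.49 if the patient is kept and 0.70³ = 0.34 if replaced.
- That the chance of at most 1 DLT in 6 measures escalation. Under this plan 1/6 is stay.

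**Conclusion.** The rule in 7.4 is wrong as written: a patient with the mandatory interruption DLT cannot meet the 75% requirement on any of the three readings tested, and 7.4, 7.11 and 17.2.1 do not agree on who is in the primary-endpoint denominator. That conclusion rests on the text and simple arithmetic. The consequence is conditional. It arises only if 7.4 is applied literally, and its size depends on q. Within the range shown, losing 25% to 50% of DLTs raises the chance of 0/3 by about 9 to 19 percentage points at a true rate of 20%, 9 to 22 at 30%, and 8 to 21 at 40%. The documents do not show that any DLT has been or would be dropped. Because the rule governs the primary endpoint and the correction costs almost nothing, it should be made.

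**What to change.** - **Sections 7.4 and 7.11:** carry over the exception in 17.2.1. A patient with a DLT is always evaluable for DLT and is never replaced, whatever dose was taken. The 75% rule applies only to patients without a DLT.
- **Section 7.4:** state which drug or drugs the 75% refers to, and use the same term in 7.11.
- **Section 7.11:** reword the and/or so that falling below 75% is not a separate ground for replacing a patient who had a DLT.

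The cost is a sentence or so in each section, with no change to any dose or treatment rule. The observed DLT rate may be slightly higher.

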- 4.1.7 Patients must have available tissue [archived formalin-fixed paraffin embedded (FFPE) blocks or fresh frozen biopsy from primary tumor or metastatic tumor biopsy] for correlative studies. Tissue source needs to be located and available at the time of registration (tissue needs to be submitted within 3 weeks of study initiation). Patients will not be able to start study drugs without tissue availability. Submission of tissue can be waived, if approved by the Study Chair in case of extraordinary/ catastrophic circumstances
- 4.1.8 Patients must have had at least one line of systemic therapy in the metastatic setting
- 4.1.9 Current use of any of the drugs listed on the Cautionary Concomitant Med list has to be approved by the Study Chair
- 4.1.10 Patients must have adequate hematologic, hepatic and renal function. All laboratory tests must be obtained within 2 weeks from study drug initiation. These include:
  - a. ANC  $\geq 1,500/\text{mm}^3$
  - b. Platelet count  $\geq 100,000/\text{mm}^3$
  - c. HgB  $\geq 9.0 \text{ g/dL}$
  - d. Creatinine clearance  $\geq 40 \text{ mL/min}/1.73 \text{ m}^2$
  - e. SGOT, SGPT  $\leq 2.5 \times \text{ULN}$  if no liver metastasis present; SGOT, SGPT  $\leq 4 \times \text{ULN}$  if liver metastasis present
  - f. Albumin  $\geq 2.0 \text{ g/dL}$
  - g. Total serum bilirubin  $\leq 1.5 \times \text{ULN}$  ( $\leq 3 \times \text{ULN}$  or direct bilirubin  $\leq 1.5 \times \text{ULN}$  if known Gilbert's syndrome)
  - h. Potassium within institutional normal limits
  - i. Phosphorus  $\leq$  institutional upper limit of normal

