## 7.5 Definition of Maximum Tolerated Dose (MTD)

The MTD will be defined as the highest dose at which 20% of the patients experienced a DLT. The first cohort of patients (3 patients) will be started at dose level 1, and each patient will be observed for 4 weeks on the specified dose. No new cohort of patients will be treated until the previous cohort has been fully evaluated for toxicity and a dose escalation decision has been made. Routine updates regarding patient and study status will be conducted.

Once the MTD is reached, the safety data will be analyzed and the expansion component of the study will be completed to assess tolerability and efficacy. Patients in the phase II portion of the study will initiate study treatment at the MTD defined in the escalation component of the trial. Note that dose reduction within patients (individually) is allowed after the 4 week DLT observation period in the escalation and in the expansion components of the study (see Dose Modification guidelines, Section 8). Intrapatient dose escalation will not be allowed. Dose reduction will be required for a given patient in case of:

- Grade 3 or 4 toxicities
- Grade  $\geq 2$  hyperphosphatemia lasting more than 21 days despite medical treatment, or
- Grade  $\geq 2$  ocular toxicity lasting more than 28 days despite medical treatment, or
- Grade  $\geq 2$  elevation of creatinine, bilirubin, AST, or ALT lasting more than 14 days despite medical treatment, or
- Grade  $\geq 2$  skin or nail toxicity for more than 28 days in a row despite optimal medical treatment, or

- Grade  $\geq$  2 GI toxicity lasting more than 14 days despite medical treatment.

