Grade 3	
 
Omit dose of palbociclib until resolved to CTCAE Grade <math>\leq</math> 1, then                     
 
- If resolved in <math>\leq</math> 7 days, then <math>\downarrow</math> 1 dose level of palbociclib.
 
- If resolved in <math>></math> 7 days and/or with signs of bleeding, then discontinue patient from palbociclib.
 
 
 

Grade 4	Discontinue palbociclib.
Bleeding	
Any bleeding (related to palbociclib) resulting in platelet transfusion	Omit dose of palbociclib until no further bleeding has been observed. Continuation of study treatment may be considered based on the thrombocytopenia recommendations.
Investigations – Hepatic	
Total bilirubin (for patients with Gilbert syndrome these dose modifications apply to changes in direct bilirubin only)	
Grade 1	Maintain dose level of palbociclib and erdafitinib.
Grade 2	
 
Omit dose of palbociclib and erdafitinib, and check bilirubin daily until resolved to CTCAE Grade <math>\leq</math> 1, then:                     
 
- If resolved in <math>\leq</math> 7 days, then maintain dose level of palbociclib and erdafitinib.
 
- If resolved in <math>></math> 7 days, then <math>\downarrow</math> 1 dose level of palbociclib and erdafitinib. Start palbociclib first, and recheck bilirubin level in 7 days. If level remains CTCAE Grade <math>\leq</math> 1, then reintroduce erdafitinib.
 
 
 

Grade $\geq$ 3	Discontinue palbociclib and erdafitinib.
Note: If CTCAE Grade 3 or 4 hyper-bilirubinemia is due to the indirect (non-conjugated) component only, and hemolysis as the etiology has been ruled out as per institutional guidelines (e.g. review of peripheral blood smear and haptoglobin determination), then $\downarrow$ 1 dose level of palbociclib and erdafitinib and continue treatment at the discretion of the Investigator.	
AST or ALT	
Grade 1	Maintain dose level of palbociclib and erdafitinib.

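### In known Gilbert's syndrome, section 7.4 judges DLT and restart on total bilirubin while 8.4 acts on direct bilirubin, so a patient back at an accepted entry value may not restart and an indirect-only Grade 2 rise can count as a DLT

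*Combined protocol and SAP*

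**What the plan says.** Criterion 4.1.10g sets a general limit of 1.5 x ULN for total bilirubin. It widens the limit "if known Gilbert's syndrome" to a total of 3 x ULN or a direct value of 1.5 x ULN.

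The bilirubin row of the 7.4 DLT table reads "CTCAE Grade 2 for > 7 consecutive days or" Grade 3 and above, and footnote c adds "Refers to total bilirubin". The event must fall in cycle 1 and be "classified as possibly, probably or definitively related to investigational study treatment". Once a DLT criterion is met, 7.4 interrupts the responsible drug.

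The hepatic row of the 7.4 follow-up table applies when treatment has been interrupted for an adverse event or laboratory value. Once total bilirubin has reached 2 x ULN, it must be measured daily until it is Grade 1 or lower before treatment may restart. The relaxation to Grade 2 for liver metastases covers AST and ALT only. The row asks for fractionation above ULN but says that follow-up does not depend on the result.

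The total bilirubin block of 8.4 states that "for patients with Gilbert syndrome these dose modifications apply to changes in direct bilirubin only". A Note to that block covers Grade 3 or 4 rises that are indirect only. Provided "hemolysis as the etiology has been ruled out as per institutional guidelines", the instruction is to go down "1 dose level of palbociclib and erdafitinib and continue treatment at the discretion of the Investigator".

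Section 7.5 requires a dose reduction for Grade 2 or higher "elevation of creatinine, bilirubin, AST, or ALT lasting more than 14 days despite medical treatment". Section 17.2.1 has a similar line for Grade 2 bilirubin lasting more than 2 weeks in the expansion component. Neither mentions Gilbert's syndrome.

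**The concern.** Eligibility and dose modification both recognise that total bilirubin can be raised in Gilbert's syndrome for reasons unrelated to drug injury. The section that defines the primary endpoint and the restart condition does not. Two things are at stake. A patient can be held off study drug at a bilirubin value that the protocol accepted at entry. And an indirect-only rise can enter the dose-escalation count as a DLT when the dose-modification rule written for that patient would leave treatment alone.

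**Working it through.** **Which fraction each rule uses in a known Gilbert's patient**

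| Rule | Fraction | Gilbert's provision |
|---|---|---|
| 4.1.10g, entry | total up to 3 x ULN, or direct up to 1.5 x ULN | yes |
| 8.4, dose modification | direct | yes |
| 7.4, DLT row and footnote c | total | none |
| 7.4, hepatic row, restart | total | none |
| 7.5 and 17.2.1, prolonged Grade 2 | not specified | none |

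**Restart.**
1. A patient may enter with a total of 2-3 x ULN (4.1.10g).
2. If treatment is interrupted and total bilirubin is at or above 2 x ULN, restart needs Grade 1 or lower (7.4 hepatic row).
3. The row starts at 2 x ULN and asks for resolution to Grade 1, so 2 x ULN must itself lie above Grade 1. The CTCAE cut-points are not printed in the documents, and this step does not need them.
4. A return to a baseline of 2-3 x ULN therefore does not meet the condition. The restart level is stricter than the entry level.
5. Under 8.4, a delay of more than 28 consecutive days due to study-related interventions requires discontinuation. If the cause is unrelated, the Protocol Chair may allow continuation. Section 7.10 limits that relief to patients beyond the first 8 weeks with clinical benefit.

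**DLT.** Take a patient whose total bilirubin worsens from baseline to Grade 2 in cycle 1, through the indirect fraction only, for more than 7 days, and suppose the event is judged possibly related.
- 7.4: total bilirubin meets the row, so this is a DLT and the responsible drug is interrupted.
- 8.4: direct bilirubin has not changed, so the Gilbert's rule asks for nothing. The indirect-only Note does not apply because it covers Grade 3 or 4 only.

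**Effect of one such DLT on escalation.** Inputs from 17.2.1: target 0.20, interval 0.15 to 0.25, cohorts of three. The prior is not stated; Beta(1,1) is assumed. After x DLTs in n patients the posterior is Beta(1+x, 1+n-x). The decision is the interval with the largest posterior probability divided by its width (0.15, 0.10 and 0.75 for E, S and D).

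| DLTs/patients | E | S | D | Decision | Table 17.2.1 |
|---|---|---|---|---|---|
| 0/3 | 3.19 | 2.06 | 0.42 | E | E |
| 1/3 | 0.73 | 1.52 | 0.98 | S | S |
| 1/6 | 1.89 | 2.72 | 0.59 | S | S |
| 1/9 | 3.04 | 3.00 | 0.33 | E | E |

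For 0/3, for example, the E entry is (1 - 0.85^4)/0.15 = 0.478/0.15 = 3.19.

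One such event in an otherwise clean first cohort changes Escalate to Stay. With cohorts of three, escalation resumes at 1/9, so 9 - 3 = 6 further DLT-free patients are needed at that dose. For scale, the synopsis total of 26 to 35 less the 20 planned for expansion leaves 26 - 20 = 6 to 35 - 20 = 15 escalation places. That split is inferred; the plan does not fix it.

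**The case against.** DLT rules and dose-modification rules serve different purposes and need not match. They differ elsewhere in this protocol: Grade 3 anemia omits palbociclib but is not a DLT unless hemolytic, and phosphorus of 7.0-9.0 mg/dL omits erdafitinib but is a DLT only if it lasts beyond 14 days despite treatment. A total-bilirubin trigger is a legitimate conservative choice, and hemolysis is a reason to keep the indirect fraction in view. Attribution also filters: an investigator may ascribe an indirect-only fluctuation to Gilbert's syndrome. Bilirubin elevation is not among the common toxicities listed for any of the three drugs.

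Most of this stands, and it keeps the point small. It does not explain a restart level below an accepted entry level. Section 8.5 lets the Protocol Chair approve departures from the Section 8 dose guidelines, but the restart condition sits in 7.4. The unrelated-cause provision helps only if the delay is so classified.

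A reader might infer more than the text supports:
- That a stable Gilbert's baseline is itself a DLT. Sections 13.2.1 and 13.3.1 require new onset or worsening. A rise that stays within Grade 2 is arguable.
- That the patient's treatment would not change at all. Section 7.4 itself interrupts the responsible drug once the DLT is met.
- That the 14-day and 2-week lines limit the conflict to certain days of cycle 1. The 7.5 provision allows individual dose reduction after the 4-week DLT period and the 17.2.1 line concerns expansion, so neither bounds it. They are a further mismatch with 8.4.
- That the sentence on fractionation creates the restart bar. It concerns follow-up; the bar comes from the total-bilirubin trigger and the Grade 1 condition.

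**Conclusion.** The inconsistency is real, confined to known Gilbert's patients, and minor. The restart problem is the firmer part: on the text alone, a patient who entered at 2-3 x ULN and is back at baseline cannot meet the 7.4 condition. Discontinuation may follow but is not automatic, since it depends on how the delay is attributed.

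The DLT problem rests on an indirect-only worsening to Grade 2 for more than 7 days in cycle 1 that is judged at least possibly related. One such event in a clean cohort moves 0/3 to 1/3, Escalate to Stay. It would be tempting to conclude that dose finding is materially biased. The documents do not support that: they give neither the share of Gilbert's patients nor the rate of such rises, so no probability can be attached, and the overall effect is likely small.

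**What to change.** 1. In the 7.4 hepatic row, let known Gilbert's patients resume when total bilirubin has returned to baseline or direct bilirubin is Grade 1 or lower.
2. Amend footnote c along these lines: *Total bilirubin; in known Gilbert's syndrome, once hemolysis has been ruled out, the Grade 2 criterion applies to direct bilirubin, as in 8.4.* Leave the Grade 3 and above criterion on total bilirubin.
3. Add the same Gilbert's wording to the prolonged Grade 2 bilirubin lines in 7.5 and 17.2.1.

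Leave the 8.4 indirect-only Note as it is. Letting the Gilbert's rule override it would remove a dose reduction at Grade 3 or 4 and would conflict with the Grade 3 or 4 reduction lines in 7.5 and 17.2.1.

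The cost is one table row, one footnote and a phrase in each of two sections. No new test is needed: 7.4 already requires fractionation above ULN, and the 8.4 Note already describes the hemolysis work-up. The price is a slightly less sensitive trigger for indirect Grade 2 rises in these few patients, limited by the hemolysis check.
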